## 1.2 Schema

Figure 1 Study Design

Pbo, placebo; R, randomization

## 1.3 Schedule of Activities

# 1.3.1 Schedule of Activities: Screening

The SoA for participants with a qualifying historical biopsy is presented in Table 2, and the SoA for participants undergoing an on-study biopsy for screening is presented in Table 3.

Table 2 Schedule of Activities in the Screening Period for Participants with a Historical Biopsy (Part A)

	Screening (procedures may occur over more than one day)
Visit	V1
Procedure/Study Day	Day-56 to -1
Informed consent (Appendix A 3)	X
Optional informed consent for Genomics Initiative research (Appendix D 2)	X
Confirmation of fasting (Section 5.3.2)	X
Inclusion and exclusion criteria (Sections 5.1 and 5.2)	X
Demography	X
Full physical examination including height and weight (Section 8.2.2)	X
Medical history (includes AUDIT questionnaire and substance usage) (Section 8.2.1)	X
Historical liver biopsy (Section 8.1.1) a	X
Serum pregnancy test (WOCBP only) (Section 8.2.5)	X
Hepatitis B and C and HIV screening (Section 8.2.5) b	X
Urinalysis for drugs of abuse (Section 8.2.5)	X
Clinical safety laboratory assessments, including eGFR and MELD score calculation (Section 8.2.5)	X
Amylase and lipase (Section 8.2.5)	X
Coagulation parameters (Section 8.2.5)	X
12-lead ECG (Section 8.2.4) °	X
Vital signs (Section 8.2.3) d	X
Assessment of AEs (Section 8.3) e	X
Concomitant medication (Section 6.5)	X
Blood sampling for ELF (Section 8.1.5)	X
FIB-4 computed score (Section 8.1.5)	X
HbA1c (Section 8.1.5)	X
Fasting serum lipid panel (Section 8.1.5)	X
Calcitonin (Section 8.2.5)	X

Table 2 Schedule of Activities in the Screening Period for Participants with a Historical Biopsy (Part A)

	Screening (procedures may occur over more than one day)
Visit	V1
Procedure/Study Day	Day-56 to -1
Check participant's ability to self-administer SC injection f	X
Demonstration of and training on self-administration of SC injection (Section 6.2) g	X
Review diet and lifestyle advice (Section 5.3.1)	X
Enrollment in IRT/RTSM	X

Participants should withhold alcohol and refrain from intense exercise for 24 hours prior to each study site visit.

- a Review of participant's medical history, including historical biopsy procedure report and histopathological findings report that meet the inclusion and exclusion criteria in Section 5.1 and 5.2. In the event the historical biopsy is deemed not evaluable and a participant screen fails, an on-study liver biopsy may be scheduled. Such an on-study biopsy, if considered, should only be performed on a date that is ≥ 180 days after the date of the historical biopsy and after all other eligibility criteria are met. Biopsy tissue and/or biopsy tissue block and/or slides should be sent for the central histopathology review laboratory to determine eligibility at least 21 days prior to planned day of randomization.
- b HbsAg, anti-HCV, HCV RNA, HIV-1 and HIV-2 antibodies.
- c ECGs will be recorded in triplicate after a 10-minute supine rest period with no more than about 2 minutes between individual ECGs, completing all 3 ECGs within a maximum of about 5 minutes. ECGs should be collected prior to vital signs, PK sample collection, or other assessments as these may alter autonomic tone.
- Whenever vital signs and blood draws are scheduled for the same nominal time, the blood draws should occur last.
- AE/SAEs will be collected from the time of signature of informed consent, throughout the treatment period and the follow-up period.
- At screening, the investigator will judge if the participant is able to self-administer SC injection.
- Activities related to demonstration and training on SC administration can be conducted at Visit 1 and/or prior to randomization at Visit 2.

AE, adverse event; AUDIT, Alcohol Use Disorder Identification Test; ECG, electrocardiogram; eGFR, estimated glomerular filtration rate; ELF, enhanced liver fibrosis; FIB-4, Fibrosis-4; HbA1c, hemoglobin A1c; HbsAg, hepatitis B surface antigen; HCV, hepatitis C virus; HIV, human immunodeficiency virus; IRT, interactive response technology; MELD, model for end-stage liver disease; PK, pharmacokinetic(s); RTSM, randomization and trial supply management; SAE, serious adverse event; SC, subcutaneous; V, visit; WOCBP, women of childbearing potential

Table 3 Schedule of Activities in the Screening Period for Participants Undergoing On-study Biopsy (Part A)

	Screening (procedures may occur over more than one day)
Visit	V1
Procedure/Study Day	Day -56 to -21 a
Informed consent (Appendix A 3)	X
Optional informed consent for Genomics Initiative research (Appendix D 2)	X
Confirmation of fasting (Section 5.3.2)	X
Inclusion and exclusion criteria (Sections 5.1 and 5.2)	X
Demography	X
Full physical examination including height and weight (Section 8.2.2)	X
Medical history (includes AUDIT questionnaire and substance usage) (Section 8.2.1)	X
Serum pregnancy test (WOCBP only) (Section 8.2.5)	X
Hepatitis B and C and HIV screening (Section 8.2.5) b	X
Urinalysis for drugs of abuse (Section 8.2.5)	X
Clinical safety laboratory assessments, including eGFR and MELD score calculation (Section 8.2.5)	X
Amylase and lipase (Section 8.2.5)	X
Coagulation parameters (Section 8.2.5)	X
12-lead ECG (Section 8.2.4) °	X
Vital signs (Section 8.2.3) d	X
Assessment of AEs (Section 8.3) e	X
Concomitant medication (Section 6.5)	X
FibroScan (Section 8.1.3) f	X
Blood sampling for ELF (Section 8.1.5) g	X
Blood sampling for NIS4 g, h	X
FIB-4 computed score (Section 8.1.5) h	X
FAST score (Section 8.1.3) g, h	X
HbA1c (Section 8.1.5)	X
Fasting serum lipid panel (Section 8.1.5)	X
Calcitonin (Section 8.2.5)	X
Check participant's ability to self-administer SC injection i	X
Demonstration of and training on self-administration of SC injection (Section 6.2) j	X

Table 3 Schedule of Activities in the Screening Period for Participants Undergoing On-study Biopsy (Part A)

	Screening (procedures may occur over more than one day)
Visit	V1
Procedure/Study Day	Day -56 to -21 a
Review diet and lifestyle advice (Section 5.3.1)	X
Enrollment in IRT/RTSM	X
Liver biopsy for histology (Section 8.1.1) a	X

Participants should withhold alcohol and refrain from intense exercise for 24 hours prior to each study site visit.

- For participants without a historical biopsy, the screening liver biopsy procedure is to be performed after all other screening procedures are complete and after confirmation that the participant meets all other inclusion/exclusion criteria. The biopsy procedure may be conducted on a different day but is part of Visit 1. Sites to ensure biopsy tissue block and/or slides are sent to the central histopathology review laboratory to determine eligibility at least 21 days prior to the planned day of randomization.
- b HbsAg, anti-HCV, HCV RNA, HIV-1 and HIV-2 antibodies.
- ECGs will be recorded in triplicate after a 10-minute supine rest period, with no more than about 2 minutes between individual ECGs, completing all 3 ECGs within a maximum of about 5 minutes. ECGs should be collected prior to vital signs, PK sample collection, or other assessments as these may alter autonomic tone.
- d Whenever vital signs and blood draws are scheduled for the same nominal time, the blood draws should occur last.
- AE/SAEs will be collected from the time of signature of informed consent, throughout the treatment period and the follow-up period.
- If a site has access to appropriate FibroScan equipment, as well as compatible software and probes, they must complete the assessments per the schedule for any participant who does not have a previous FibroScan assessment conducted within 90 days of initiating screening activities. If not and the assessment cannot be conducted, this will not constitute a deviation from the protocol. Fibroscan study must be performed in a fasting state.
- A pre-biopsy screening strategy prior to conduct of on-study liver biopsy, using a sequential combination of the following, namely, BMI, FIB-4, NIS4 (if available), FAST score or FibroScan, ELF, is strongly recommended. Investigator may choose an alternative pre-biopsy screening strategy that may not include one or more of the above parameters. It is recommended that investigators discuss the alternative pre-biopsy screening strategy with the sponsor prior to conduct of on-study biopsy.
- h FAST score will be calculated only at sites that have the required software.
- At screening, the investigator will judge if the participant is able to self-administer SC injection.
- Activities related to demonstration and training on SC administration can be conducted at Visit 1 and/or prior to randomization at Visit 2.

AE, adverse event; AUDIT, Alcohol Use Disorder Identification Test; BMI, body mass index; ECG, electrocardiogram; eGFR, estimated glomerular filtration rate; ELF, enhanced liver fibrosis; FAST, FibroScan-AST; FIB-4, Fibrosis-4; HbA1c, hemoglobin A1c; HbsAg, hepatitis B surface antigen; HCV, hepatitis C virus; HIV, human immunodeficiency virus; IRT, interactive response technology; MELD, model for end-stage liver disease; NIS4, non-invasive diagnostic score 4; PK, pharmacokinetic(s); RTSM, randomization and trial supply management; SAE, serious adverse event; SC, subcutaneous; V, visit; WOCBP, women of childbearing potential

# 1.3.2 Schedule of Activities: Treatment Period and Follow-up

## 1.3.2.1 Part A Schedule of Activities: Treatment Period and Follow-up

Table 4 Schedule of Activities for Part A: Treatment Period and Follow-up

	Treatment Period											
Week	0	4	8	12	16	20	24	32	40	48		Follow-up
Visit	V2	V3	V4	V5	V6	V7	V8	V9	V10	V11 (EOT)	E/D Visit b	4 weeks after EOT or E/D (± 5d) a
Day (visit window ± x days) a	1	29 ± 5d	57 ± 5d	85 ± 5d	113 ± 5d	141 ± 5d	169 ± 5d	225 ± 5d	281 ± 5d	337 ± 5d		
Confirmation of fasting (Section 5.3.2)	X									X	X	
Demonstration of and training on self- administration of SC injection (Section 6.2) °	X											
Review of adherence to diet and lifestyle advice (Section 5.3.1)	X	X	X	X	X	X	X	X	X	X	X	X
Concomitant medication (Section 6.5)	X	X	X	X	X	X	X	X	X	X	X	X
12-lead dECG (Section 8.2.4) d	X	X	X	X	X	X	X	X	X	X	X	X
Vital signs (Section 8.2.3) e	X f	X	X	X	X	X	X	X	X	X	X	X
Abbreviated (symptom-directed) physical examination including weight (Section 8.2.2, Section 8.1.4)	X	X	X	X	X	X	X	X	X	X	X	X
Assessment of AEs and injection site reactions (Section 8.3; Section 8.2.6.1) g, h	X	X	X	X	X	X	X	X	X	X	X	X
Clinical safety laboratory assessments, including eGFR and MELD score calculation (Section 8.2.5)	X	X	X	X	X	X	X	X		X	X	X
Amylase and lipase (Section 8.2.5)	X						X	X		X	X	X
Coagulation parameters (Section 8.2.5)	X						X	X		X	X	X
Calcitonin (Section 8.2.5)	X									X	X	

Table 4 Schedule of Activities for Part A: Treatment Period and Follow-up

	Treatment Period											
Week	0	4	8	12	16	20	24	32	40	48		Follow-up
Visit	V2	V3	V4	V5	V6	V7	V8	V9	V10	V11 (EOT)	E/D Visit b	4 weeks after EOT or E/D (± 5d) a
Day (visit window ± x days) a	1	29 ± 5d	57 ± 5d	85 ± 5d	113 ± 5d	141 ± 5d	169 ± 5d	225 ± 5d	281 ± 5d	337 ± 5d		
Urine pregnancy test (WOCBP only) (Section 8.2.5)	X			X			X			X	X	X
Liver biopsy for histology (Section 8.1.1)										X i	X j	
FibroScan, LSM, CAP, FAST Score, Agile 3+ (Section 8.1.3) k,1	X									X	X	
Randomization in IRT/RTSM (Section 6.3)	X											
Study intervention administration in clinic m	X	X	X	X	X	X	X	X	X			
Study intervention dispensed for at home administration	X	X	X	X	X	X	X	X	X			
Instructions for use dispensed	X	X	X	X	X	X	X	X	X			
Uptitration step for 300 µg cotadutide/placebo		X	X	X								
Uptitration step for 600 µg cotadutide/placebo		X	X	X	X	X	X					
Study intervention compliance (Section 6.4)		X	X	X	X	X	X	X	X	X	X	
Urine for albumin and creatinine	X			X			X			X	X	
HbA1c (Section 8.1.5)	X			X			X			X	X	
Fasting serum lipid panel (Section 8.1.5)	X									X	X	
Pre-dose blood for PK analysis (Section 8.4)	X	X		X			X			X	X	X
Serum for immunogenicity (ADA) (Section 8.4.2)	X	X		X			X			X	X	X
Blood sampling for ELF (Section 8.1.5)	X									X	X	

Table 4 Schedule of Activities for Part A: Treatment Period and Follow-up

				ŗ	Freatmen	nent Period						
Week	0	4	8	12	16	20	24	32	40	48		Follow-up
Visit	V2	V3	V4	V5	V6	V7	V8	V9	V10	V11 (EOT)	Visit b 4 weeks after EO	4 weeks after EOT or E/D (± 5d) a
Day	1	29	57	85	113	141	169	225	281	337		
(visit window $\pm x$ days) a	1	± 5d	± 5d	± 5d	± 5d	± 5d	± 5d	± 5d	± 5d	± 5d		
Blood sampling for Pro-C3 (Section 8.1.5)	X									X	X	
FIB-4 computed score (Section 8.1.5)	X									X	X	
Blood for fasting plasma glucose-(Section 8.1.5)	X									X	X	
Blood for C-peptide (Section 8.1.5)	X									X	X	
Blood for adiponectin (Section 8.1.5)	X									X	X	
Genomics Initiative optional, exploratory genetic sample (Section 8.6, Appendix D) °	X											
Optional biomarker serum sample (for biomarker research) (Section 8.5.2)	X									X	X	

Participants should withhold alcohol and refrain from intense exercise for 24 hours prior to each study site visit.

- Visit windows should be calculated from Day 1. Visit 2 (randomization) may be scheduled any day following confirmation that participant meets all eligibility criteria including eligibility reading from the central pathology review of the biopsy (historical or on-study) sample and laboratory report assessments from the central laboratory (eg, the screening period does not need to be a full 8 weeks). Follow-up visit conducted 4 weeks (± 5 d) after EOT visit or E/D visit. For participants who discontinue study intervention permanently and do not continue with study visits, follow-up visit should be performed 4 weeks (± 5 d) after the E/D visit. For participants who discontinue study intervention early but continue with study visits, follow-up visit should be performed 4 weeks (± 5 d) after the EOT.
- b Performed in event of early discontinuation of study intervention or withdrawal from study.
- c Activities related to demonstration and training on SC administration can be conducted at Visit 1 and/or prior to randomization at Visit 2.
- ECGs will be recorded in triplicate after a 10-minute supine rest period, with no more than about 2 minutes between individual ECGs, completing all 3 ECGs within a maximum of about 5 minutes. ECGs should be collected prior to vital signs, PK sample collection, or other assessments as these may alter autonomic tone.
- Whenever vital signs and blood draws are scheduled for the same nominal time, the blood draws should occur last.
- At Visit 2, vital signs should be assessed prior to first dose of study intervention.
- g AE/SAEs will be collected from the time of signature of informed consent, throughout the treatment period and follow-up period.
- Assessment of injection site reactions to be conducted after injection of study intervention.

-  The post-baseline biopsy to occur within a window from -2 weeks prior to Visit 11 (Week 48) until 4 weeks after Visit 11.
- Biopsy should only be conducted as part of the E/D visit activities in participants who have received study intervention for at least 36 weeks and who are unwilling or unable to wait until Week 48. For participants who continue the study after an E/D visit and have a biopsy at the E/D visit, an additional biopsy should not be collected at Week 48. Biopsy should be scheduled within -2 weeks prior to +4 weeks after the E/D visit.
- If a site has access to appropriate FibroScan equipment, as well as compatible software and probes, they must complete the assessments per the schedule with extended visit windows. For V2, FibroScan must be performed pre-dose within extended visit window of -14 days but only for participants who meet all inclusion/exclusion criteria (including histology central read) and are determined to be eligible for randomization. For all other visits, Fibroscan must be performed within extended visit window of ±14 days. If a site does not have access to appropriate FibroScan equipment, as well as compatible software and probes, and the assessment cannot be conducted, this will not constitute a deviation from the protocol. FibroScan should be conducted in a fasting state.
- FAST score will be calculated only at sites that have the required software.
- Study intervention should be administered after all assessments have been conducted and samples have been collected.
- ADA samples will be collected prior to administration of IP.
- Genomics sample: If for any reason, the sample is not drawn at Visit 2, it may be taken at any visit until the last study visit. Only one sample should be collected per participant for genetics during the study. The optional informed consent for Genomics Initiative research must be signed prior to sample collection. Refer to Appendix D for inclusion/exclusion criteria specific to the Genomics Initiative and further details on the optional Genomics Initiative sample.

ADA, anti-drug antibody; AE, adverse event; CAP, controlled attenuation parameter; dECG, digital electrocardiogram; E/D, early study intervention discontinuation; ECG, electrocardiogram; eGFR, estimated glomerular filtration rate; ELF, enhanced liver fibrosis; EOT, end of treatment; FAST, FibroScan-AST; FIB-4, fibrosis-4; HbA1c, hemoglobin A1c; IP, investigational product; IRT, interactive response technology; LSM, liver stiffness measurement; MELD, model for end-stage liver disease; PK, pharmacokinetic(s); Pro-C3, released N-terminal propeptide of type III collagen; RTSM, randomization and trial supply management; SAE, serious adverse event; V, visit; WOCBP, women of childbearing potential

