### 1.3.4 Unscheduled Visit for Safety or Any Other Reason

Unscheduled visits for safety or any other reason may be initiated as needed, at the discretion of the investigator. A list of activities for unscheduled safety visits is presented in Table 6.

Table 6 Schedule of Activities for Unscheduled Visit for Safety or Any Other Reason

	Unscheduled Safety Visit
Review of adherence to diet and lifestyle advice (Section 5.3.1)	X
Concomitant medication (Section 6.5)	X
Clinical safety laboratory assessments based on clinical judgment (Section 8.2.5)	X
Vital signs (Section 8.2.3) a	X
Abbreviated (symptom-directed) physical examination including weight (Section 8.2.2; Section 8.1.4)	X
Assessment of AEs and injection site reactions (Section 8.3; Section 8.2.6.1) b, c	X
Study intervention administration in clinic d	X

Participants should withhold alcohol and refrain from intense exercise for 24 hours prior to each study site visit.

AE, adverse event; SAE, serious adverse event

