# 7 DISCONTINUATION OF STUDY INTERVENTION AND PARTICIPANT DISCONTINUATION/WITHDRAWAL

# 7.1 Discontinuation of Study Intervention

It may be necessary for a participant to permanently discontinue (definitive discontinuation) study intervention. Participants who discontinue study intervention early will have an early discontinuation visit as described in the SoA (Section 1.3). After the early discontinuation visit, participants will be encouraged to remain in the study for all remaining visits and study procedures as outlined in the SoA, with the exception of the urine pregnancy test, dispensation of study intervention and Instructions for Use, and PK sampling. Participants will be encouraged to have the biopsy at Week 48 as planned in the SoA. Participants who are unwilling or unable to wait until Week 48 will have the biopsy procedure as part of the early discontinuation visit if they have received study intervention for at least 36 weeks. Samples for clinical safety laboratory assessments, amylase and lipase, coagulation parameters, and calcitonin do not need to be collected at visits occurring more than 30 days after discontinuation of study intervention except as needed for lab abnormalities/AEs that require follow-up to resolution.

Note that discontinuation from study intervention is NOT the same thing as a withdrawal from the study.

An individual participant will not receive any further IP if any of the following occur:

- Withdrawal of consent/assent from further treatment with IP.
- Lost to follow-up.
- Noncompliance that, in the opinion of the investigator or sponsor, warrants withdrawal (eg, refusal to adhere to scheduled visits).
- Pregnancy in a female participant.
- An AE that, in the opinion of the investigator or the sponsor, contraindicates further dosing; specific examples include:
  - Clinically significant tachyarrhythmias, including but not limited to life-threatening arrhythmia, eg, sustained ventricular tachycardia or ventricular fibrillation.
  - Acute pancreatitis

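### Participants who stop IP but stay in the study may have no required repeat safety labs after the E/D panel, and WOCBP who stay have no later scheduled pregnancy test

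*Protocol*

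**What the plan says.** **E/D visit.** Protocol Section 7.1: "Participants who discontinue study intervention early will have an early discontinuation visit as described in the SoA". Table 4 footnote b agrees: "Performed in event of early discontinuation of study intervention or withdrawal from study". The E/D column of Table 4 carries chemistry and haematology, amylase and lipase, coagulation, calcitonin and, for WOCBP, a urine pregnancy test.

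**Follow-up visit.** The follow-up column of Table 4 repeats these tests except calcitonin. For those who stop and leave, footnote a says "follow-up visit should be performed 4 weeks (± 5 d) after the E/D visit". For those "who discontinue study intervention early but continue with study visits, follow-up visit should be performed 4 weeks (± 5 d) after the EOT", that is about Day 365.

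**Waiver and exception.** Section 7.1 names calcitonin, coagulation, amylase and lipase, and the clinical safety labs, and says of these samples: "do not need to be collected at visits occurring more than 30 days after discontinuation of study intervention except as needed for lab abnormalities/AEs". The exception covers problems still being followed until they resolve. Stayers are encouraged to attend all remaining visits "with the exception of the urine pregnancy test", among other items.

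**Lab schedule.** Table 4 has no safety labs at Week 40, and no amylase, lipase or coagulation between Day 1 and Week 24.

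**The concern.** Completers and leavers have safety labs and a pregnancy test about 4 weeks after their last treatment visit. Stayers have them only where a regular lab visit happens to fall soon after stopping, because footnote a moves their follow-up visit to a time when the waiver usually removes the labs. Section 7.1 removes their later pregnancy tests outright. The protocol gives no reason for the difference, and these are the participants it encourages to remain.

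Safety is the primary objective, and drug-induced liver injury, pancreatitis and acute renal failure are adverse events of special interest (Section 8.3.6). A new silent rise in ALT, lipase or creatinine after a normal E/D panel would not prompt a for-cause sample. A conception shortly before the last dose may not show at E/D.

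**Working it through.** The documents give no figure on this point, so there is none to reproduce.

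**Inputs** (protocol Table 4, nominal days)
- Chemistry/haematology: Days 29, 57, 85, 113, 141, 169, 225, 337.
- Amylase, lipase, coagulation: Days 169, 225, 337.
- Waiver limit: 30 days after stopping (Section 7.1).
- Last-dose day d = 1 to 336, with E/D on day d + L.
- Assumptions: every d equally likely (the documents give no distribution), and L = 0 at first.

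**Rule.** A repeat is required if some lab day x satisfies d + L < x ≤ d + 30.

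**Chemistry/haematology, L = 0**
- Up to Day 169 lab visits are 28 days apart, so every d from 1 to 168 has a repeat: gap 0 of 168.
- After Day 169 the next lab is Day 225, which counts only from d = 225 − 30 = 195. Gap: Days 169–194, 26 days.
- After Day 225 the next lab is Day 337, which counts only from d = 337 − 30 = 307. Gap: Days 225–306, 82 days.
- Total 26 + 82 = 108; 108/336 = 32.1%, and 108/168 = 64.3% from Day 169 on.

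**Amylase, lipase, coagulation, L = 0**
- The first lab after Day 1 is Day 169, which counts only from d = 169 − 30 = 139. Gap: Days 1–138, 138 days (138/168 = 82.1%).
- From Day 169 the gap is the same 108 days.
- Total 138 + 108 = 246; 246/336 = 73.2%.

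**Example.** Last dose and E/D panel on Day 225; Day 281 has no labs; Day 337 is 112 days after stopping and is waived.

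**Sensitivity**
- Visits shifted independently by −5, 0 or +5 days: 106–137 of 336 (32–41%) and 246–251 of 336 (73–75%).
- E/D 7 days after the last dose (L = 7): 154 of 336 (46%) and 267 of 336 (79%). Of the 154, 32 lie before Day 169. Here the E/D panel is itself a sample taken after stopping.
- Counting the Day 365 follow-up changes nothing at L = 0. At L = 7 it removes Days 335 and 336, giving 152 and 265.
- If 80% of stops fall in Days 1–168: chemistry 0.2 × 64.3% = 12.9%; amylase, lipase and coagulation 0.8 × 82.1% + 0.2 × 64.3% = 78.6%.

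**Leavers.** Their follow-up is nominally L + 28 days after the last dose. Read literally, the waiver reaches it when L + 28 > 30, that is L > 2.

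**Number of people.** Assume 10–30% of about 55 stop early and half of these stay: 55 × 0.10 × 0.5 = 2.75 to 55 × 0.30 × 0.5 = 8.25 stayers. Times 108/336 gives 0.9–2.7 without repeat chemistry; times 246/336 gives 2.0–6.0 without repeat amylase, lipase and coagulation.

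**The case against.** **No passage requires a repeat panel within 30 days of stopping.** True as a general rule. But Table 4 and footnote a set the standard themselves: completers and leavers have a 4-week check.

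**Monitoring on drug is just as sparse.** This stands in part. Of the 246 days for amylase, lipase and coagulation, 138 come from the Day 1–169 interval that applies to everyone, so the 73% is not all due to the rules for stayers.

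**Much remains in place.** This also stands. Section 7.1 keeps labs for known abnormalities and adverse events, Table 6 allows unscheduled labs on clinical judgment, and adverse event, ECG, vital-sign and physical checks continue. Contraception is required throughout the study (Section 5.1).

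**Stronger readings a reader might infer, which the documents do not support:**
- *Stayers go untested after stopping.* They have the full E/D panel and a pregnancy test.
- *A third or three quarters of participants are affected.* The percentages are shares of stop days. Dose escalation ends at Week 12 or 24, and participants who cannot reach 200 µg must stop (Section 6.6). Stops may therefore cluster early, which would lower the chemistry figure.
- *The chemistry gap arises only from Week 24.* That holds for nominal visits with E/D on the last-dose day, not once E/D lags.
- *The SAP's on-treatment liver window is left empty.* SAP 3.3.1.2 classifies results and does not require collection. An E/D panel within 30 days of stopping already supplies a liver test in that window.
- *A planned output is undermined.* SAP 4.5.3.2 bases laboratory tables on on-study data, so the 7-day on-treatment limit does not govern them.

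**Conclusion.** The point holds as a limited gap in patient follow-up. Stayers have a full E/D panel, but footnote a and Section 7.1 together may leave them with no required repeat safety labs. WOCBP who stay have no scheduled pregnancy test after E/D.

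The 108 and 246 of 336 stop days rest on E/D on the last-dose day, nominal visits and evenly spread stops. The count of perhaps 1–3 participants for chemistry and 2–6 for amylase, lipase and coagulation also rests on assumed stopping and staying rates. The exposure is confined to new silent laboratory changes and undetected pregnancy after E/D. No planned result becomes wrong. This is a cheap improvement worth making, not a flaw in the analysis.

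**What to change.** Amend Section 7.1 and Table 4 footnote a along these lines: *Participants who stop IP and continue with study visits have clinical safety labs, amylase and lipase, coagulation and, for WOCBP, a urine pregnancy test once more, at the first scheduled visit at least 3 weeks after the last dose, moved within its window where possible. The 30-day laboratory waiver and the pregnancy-test exception apply only after this check. The waiver does not apply to the 4-week follow-up visit of participants who leave.*

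**Timing.** Using Days 29 to 337 plus the follow-up at Day 365, the check falls within 30 days of the last dose for 8 (Day 29) + 8 × 10 (Days 57–337) + 2 (Day 365) = 90 of 336 stop days at nominal visits. If visits move by up to 5 days it is 13 + 8 × 20 + 7 = 180. The longest wait is 76 days (last dose Day 149, check Day 225), or 66 days with movement (Day 154 to Day 220).

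**Cost.** Extra tubes and a dipstick at one existing visit for a handful of participants, with no added visits. The amendment needs ethics and regulatory approval (Appendix A 1). Liver results later than 30 days count as on-study, not on-treatment, so they do not enter the on-treatment liver categories or the eDISH plots. The SAP needs no change.
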